6. GENERAL ANALYSIS DEFINITIONS

6.1 TREATMENT(S)

The starting dose of the study is BI 836880 40 mg every week, and dose escalation decision will be made by Data Safety Board (DSB).

The following treatment period will be defined:

- Screening: from the date of informed consent to the date of first study medication intake -1 day.
- On-treatment: from the date of first intake of study drug to the date of last study drug administration + 42 days, i.e., actual on-treatment period + residual effect period (REP).
- Post-study: from the last day of on-treatment period + 1 day onwards

6.2 IMPORTANT PROTOCOL VIOLATIONS

A protocol violation (PV) is important if it affects the rights or safety of the study patients, or if it can potentially influence the primary outcome measurements in a non-negligible way. Patients with important PVs that could potentially impact the evaluation of the primary endpoint(s) will be excluded.

A list of important PVs is given in Table 6.2: 1 below. Important PVs will be reviewed at Medical Quality Review Meetings (MQRMs) conducted periodically during the trial. A list of protocol deviations will be discussed at the blinded report planning meetings (BRPMs).

If the data show other important PVs, this table will be supplemented accordingly at MQRMs or BRPMs or through team review of the manual PV log. The decision whether a patient will be excluded from the analysis will be made at the final BRPM prior to DBL.

Table 6.2: 1 Important protocol violations

| Category / | | Description | Requirements | Excluded | |
|------------|------|--------------------------------------|---|----------|--|
| Cod | le | | | from | |
| A | | Entrance criteria not met | | | |
| | A1 | Inclusion criteria not met | | | |
| | A1.1 | Requirements on age or birth control | Inclusion criteria 1 or 8 | None | |
| | | not met | | | |
| | A1.2 | Disease severity not met | Inclusion criteria 2 | None | |
| | A1.3 | Adequate health condition not met | Inclusion criteria 3, 4, 6, or 7 | None | |
| | A2 | Exclusion criteria not met | | | |
| | A2.1 | Hypersensitivity to the trial drug | Exclusion criteria 1 | None | |
| | A2.2 | Previous anti-cancer therapy | Exclusion criteria 2 | None | |
| | | washout period not met | | | |
| | A2.3 | Clinically relevant concomitant or | Exclusion criteria 3, 4, 5, 6, 7, 8, 9, 10, or 11 | None | |
| | | history of disease, pre-existing | | | |
| | | conditions | | | |

Table 6.2: 1 Important protocol violations (cont.)

| Cate | egory / | Description | Requirements | Excluded from |
|---|------------------------------|---|---|---------------|
| A | | Entrance criteria not met | | HOIII |
| | A2.4 | Under judicial protection and legally institutionalized | Exclusion criteria 12 | None |
| A2.5 Requirement of adherence to protocol not met | | 1 * | Exclusion criteria 13 | None |
| | | | Exclusion criteria 14 | None |
| В | | Informed consent | | |
| | | | Informed consent date missing | All |
| | B2 Informed consent too late | | Informed consent date was after screening visit date | None |
| С | | Trial medication and randomisation | | |
| | C1 | Incorrect trial medication taken | To be determined on a case by case basis. Listing will be created and decision will be made at MQRM / BRPM, e.g., incorrect dose taken, dose in course 1 not following dose escalation scheme, overdose, use of expired medication etc. | None |
| | С3 | Non-compliance | Study drug not taken according to protocol. To be determined on a case by case basis. Listing will be created and decision will be made at MQRM / BRPM e.g., outside of dosing schedule window, unreasonable drug administration time, etc. | None |
| | C5 | Re-treatment criteria not met | Re-treatment criteria was not met according to CTP section 4.1.4 | None |
| D | | Concomitant medication | | |
| | D2 | Prohibited medication use | Refer to CTP section 4.2.2.1. | None |
| Z | | Other | | |
| | Z3 | Missing critical safety information in cycle 1 | Essential safety information for the evaluation of DLT is missing | None |

6.3 PATIENT SETS ANALYSED

Treated set

This patient set includes all patients enrolled in the trial who were documented to have taken at least one dose of study medication.

Dose finding cohort treated set:

This patient set includes all patients enrolled in dose finding and confirmation of MTD cohort of the trial who were documented to have taken at least one dose of study medication and were evaluable for the MTD determination.

MTD Expansion cohort treated set:

This patient set includes all patients enrolled in expansion cohort of the trial who were documented to have taken at least one dose of study medication.

Tumor type expansion treated cohort set

This patient set includes all patients with selected tumor type enrolled in expansion cohort of the trial who were documented to have taken at least one dose of study medication.

6.5 POOLING OF CENTRES

This section is not applicable.

6.6 HANDLING OF MISSING DATA AND OUTLIERS

Missing or incomplete AE dates are imputed according to BI standards (see "Handling of missing and incomplete AE dates") (3). Missing data and outliers of PK data are handled according to (2). Please refer to section 7.5 of the CTP for more details.

6.7 BASELINE, TIME WINDOWS AND CALCULATED VISITS

Baseline values will be the measurements taken most recently prior to first administration of study drug (same dates are allowed). If not available, then the values reported at the screening visit will be considered. For lab values, baseline is the one observed closest but prior to or on the first day of drug intake.

Time windows and visits will be calculated to determine the planned day of tumour measurement and response status, based on the protocol-specified tumour imaging schedule. Imaging data will be displayed as screening, and then every 6 weeks i.e.: Week 6, 12, 18... etc. The number of weeks will be calculated using their relative day (from start of treatment) using a ± 3 week window (images taken in the first 3 weeks from start of treatment will be

assigned to Week 6). Imaging not older than 28 days at start of treatment will suffice as screening images and do not need to be repeated.

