Name of finished product	:	Not applicable			
Name of active ingredient	:	BI 836880			
Protocol date:	Trial number:		Revision date:		
10 Dec 2015	1336.6		13 Mar 2019		
Main criteria for inclusion:	 Age ≥ 18 years Histologically or cytologically confirmed malignancy which is locally advanced or metastatic solid tumor, and either refractory after standard therapy for the disease or for which standard therapy is not reliably effective, e.g. patients do not tolerate or have contraindications to otherwise available standard therapy and tumour lesions evaluable for Dynamic contrast-enhanced (DCE) MRI at MTD ECOG performance status ≤2 Adequate hepatic, renal and bone marrow functions Life expectancy ≥ 3 months in the opinion of the investigator Recovery from all reversible adverse events of previous anti-cancer therapies to baseline or CTCAE grade 1, except for alopecia (any grade) and sensory peripheral neuropathy CTCAE grade < 2 				
Test product(s):	BI 836880 and Diluen	t for BI 836880			
dose:	Starting dose of 40 mg	g weekly infusion			
mode of administration:	Intravenous weekly in	a 21-day treatment course			
Comparator products:	Not applicable				
dose:	Not applicable				
mode of administration:	Not applicable				
Duration of treatment:	Continuous treatment toxicity	in the absence of disease progression	on or unacceptable		
Endpoints	Primary endpoint				
Safety criteria:		ling to Common Terminology Crite se limiting toxicities, physical exam , ECOG			
Statistical methods:		ratory statistics analyses. Dose esca ession model with over dose control			

FLOW CHART COURSE 1

Trial periods	Screening		Т	reatment cou	ЕОТ*	EoR*	FU**		
Course				1					
Visit	Screen		V1		V2	V3			
Day	-21 to -1	1	2	3	8 + 2	15 + 2		EoT+42 d	
Informed consent ¹	x								
Demographics	x								
Medical history	X								
Inclusion/exclusion criteria	X	Х							
Physical examination ²	X	Х	х	X	X	х	Х	х	
Height	X								
Weight	X	Х					х		
Body temperature ³	x	Х	х		Х	х	Х		
Blood pressure ⁴ , heart rate	X	х	х	X	X	х	Х	х	
ECOG performance status	x	Х					Х		
Administration of BI 836880 infusion		Х			Х	х			
Safety Lab parameters ⁵	x	Х			Х	х	Х		
Pregnancy test	X	Х					Х		
Tumor assessment ⁶	x						Х		Х
12-lead ECG ⁷	x	х	х		Х	х	Х		
Echocardiography ⁸	x						х		
Pharmacokinetics ⁹		х	х	X	Х	х	х	Х	x (FU1)
Anti-drug antibodies ¹⁰		х					Х	х	x (FU1)

Trial Protocol

Page 5 of 99

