⁵Haematology, biochemistry and coagulation parameters will be performed locally. Previous safety lab: investigations are acceptable if performed within 72 hours prior to the first treatment administration. For details see Section 5.3.3 After the interim data base lock safety laboratory tests will be performed at investigator's discretion based on the standard medical care. Findings will be documented in the eCRF only if qualifying as (S)AE

⁶Tumor assessment will be performed every 6 weeks after start of treatment with BI 836880 (in the week preceding the start of treatment course 3, 5, 7, 9, 11...) and should include CT scans or MRI. Imaging not older than 28 days at start of treatment will suffice as screening images and don't have to be repeated. The EOT tumor assessment is optional if performed in the previous 4 weeks. In the event of any treatment interruption or treatment delay, the tumor assessment should follow the original schedule

After the interim data base lock, frequency of tumor assessment may be adapted according to local standard of care and in agreement with the sponsor if the patient is deriving clinical benefit (e.g. CR, PR or SD > 6 months).

Boehringer Ingelheim BI Trial No.: 1336.6 c03124055-06

Soehringer Ingelheim 13 Mar 2019

Trial Protocol Page 8 of 99

Proprietary confidential information © 2019 Boehringer Ingelheim International GmbH or one or more of its affiliated companies

After the interim data base lock, ECG will be performed as clinically indicated on local machine and the assessment will be done by the investigator. Shipment of ECGs to central vendor is no longer required

⁸Echocardiography will be performed locally at screening (not older than 7 days before start of treatment) and at EoT. During treatment period, echocardiography will be conducted only if clinically indicated. After the interim data base lock findings related to echocardiography will be reported in the eCRF only if qualifying as (S)AE

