5.3.2 Vital Signs

Vital signs (blood pressure, heart rate and body temperature) will be recorded at every visit indicated in the flow chart.

At day of administration two time points will be evaluated:

- 1- At pre-dose (-60 minutes to 5 minutes)
- 2- Shortly before the end of infusion

In case of an infusion-related reaction, if deemed necessary, the investigator should decide for intensive monitoring of vital signs.

Blood pressure

Systolic and diastolic blood pressure as well as pulse rate (electronic or by palpation, count for 1 minute) will be measured after 5 minutes of rest in seated position. The blood pressure measurement should be performed three times at each time point and values of these measurement will be entered in the CRF (refer to Appendix 10.2 and Appendix 10.4) After the interim data base lock blood pressure is no longer mandatory at specific visits but will be performed at the investigator's discretion. Findings will be documented in the eCRF only if qualifying as (S)AE

Body temperature

Whenever possible the same method should be used for body temperature measurement in one patient. All methods used should deliver valid reproducible results according to common clinical practice.

Body temperature > 38°C must be re assessed 1 hour after, especially in cases of suspected febrile neutropenia (see CTCAE V.4.03).

After the interim data base lock body temperature is no longer mandatory at specific visits but will be performed at the investigator's discretion. Findings will be documented in the eCRF only if qualifying as (S)AE

Page 40 of 99

Proprietary confidential information © 2019 Boehringer Ingelheim International GmbH or one or more of its affiliated companies

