5.3.3 Safety laboratory parameters

Blood sample for assessment of safety laboratory examinations have to be collected at the time points specified in the Flow Chart, but should be more frequent in case of relevant findings, e.g. in case of grade 4 neutropenia, as any non-proven recovery within 7 days will be counted as DLT or proteinurea, for which determination of CTCAE grade 2 versus grade 3 needs to be done by quantitative measurement.

Safety laboratory examination will include haematology, biochemistry, coagulation, and urine analysis.

- **Haematology**: Haemoglobin, red blood cell count (RBC), white blood cell count (WBC) and differential, platelets.
- **Biochemistry**: glucose, sodium, potassium, calcium, magnesium, inorganic phosphate, creatinine, aspartate amino transferase (AST), alanine amino transferase (ALT), alkaline phosphatase, lactate deshydrogenase (LDH), bilirubin, urea, total protein, albumin, uric acid, CK, CK-MB.
 - Serum immunoglobulin levels (IgG, IgM, IgA, IgE) and direct antiglobulin test have to be measured at screening and at occurrence of infusion related reactions.
- Coagulation: activated partial thromboplastin time (aPTT), prothrombin time (PT) or international normalised ratio (INR) where indicated (e.g. treatment with vitamin K antagonists)
- Urinalysis: pH, glucose, leukocytes, erythrocytes, protein, nitrite will be analysed primarily qualitatively by dipstick. In case of pathological findings, further evaluation should be performed and the findings documented. A positive urine dipstick for protein of ≥ 2+ has to be followed by a determination of urine protein to creatinine ratio (UPCR) in a morning spot urine sample. In case of a ratio ≥ 0.5, a 24-hour urine collection for protein loss has to be performed. The 24 hour urine collection will be repeated every time the UPCR is ≥ 0.5 as often as clinically indicated.

After the interim data base lock, safety laboratory tests (haematology, biochemistry, coagulation, urinalysis) will be performed at the investigator's discretion based on the standard medical care. Findings will be recorded in the e-CRF only if qualifying for (S)AE/AESI.

Pregnancy test: a serum pregnancy test will be performed as outlined in the Flow Chart in women of childbearing potential.

Previous laboratory investigations performed within 72 hours prior to the first treatment administration visit are acceptable to confirm the patient eligibility.

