7.5 HANDLING OF MISSING DATA

No imputation will be performed on missing efficacy data.

Missing baseline laboratory values will be imputed by the respective values from the screening visit. No other imputations will be performed on missing data although every effort

Trial Protocol

Page 64 of 99

Proprietary confidential information © 2019 Boehringer Ingelheim International GmbH or one or more of its affiliated companies

will be made to obtain complete information on all adverse events and to follow-up the patients for efficacy data.

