7.8.2 Laboratory data

The analyses of laboratory data will be descriptive in nature and will be based on BI standards "Display and Analysis of Laboratory Data" (7). CTC grade for applicable lab parameters will be calculated according to CTCAE v4.0 (6).

Descriptive statistics of all converted laboratory values by visit will be provided including changes from baseline. Frequency tables of transitions relative to the reference range and of possible clinically significant abnormalities will be produced. For those parameters that have CTC grading possible clinically significant abnormalities are defined as those laboratory values with a CTC grade ≥ 2 that have had an increase of ≥ 1 grade from baseline. For those parameters for which no CTC grade has been defined standard BI project definitions will be used to decide on clinical significance. Further frequency table will show the transition of CTC grade from baseline to worst value and last value on treatment.

Summaries will be produced of laboratory data recorded prior to treatment, on-treatment and post-treatment. For details on the treatment definition, see section 6.1.

The focus of the laboratory data analysis will be on the following laboratory parameters:

• Low values: Activated Partial Thromboplastin Time (aPTT), Prothrombin Time (PT), International Normalised Ratio (INR), White Blood Cell Count (WBC) with differential, Platelets (PLT)

• High values: Aspartate Aminotransferase (AST), Alanine Aminotransferase (ALT), bilirubin, Alkaline Phosphatase (AP), Activated Partial Thromboplastin Time (aPTT), Prothrombin Time (PT), International Normalised Ratio (INR), Protein levels in urine

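### The laboratory baseline rule in SAP 6.7 goes by date only, so a Day 1 sample drawn after the first infusion has started can become baseline; the clear case is the reaction sample after a first-infusion reaction

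*SAP*

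**What the plan says.** SAP 6.7 contains two baseline rules. The general one is: "Baseline values will be the measurements taken most recently prior to first administration of study drug (same dates are allowed". If no such value exists, screening is used. Laboratory data then get a sentence of their own: "For lab values, baseline is the one observed closest but prior to or on the first day of drug intake".

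The protocol's Course 1 flow chart marks "Safety Lab parameters" at screening and on Days 1, 8 and 15, with no clock time for Day 1. Footnote 5 adds that earlier "investigations are acceptable if performed within 72 hours prior to the first treatment administration". Under biochemistry, protocol 5.3.3 requires serum immunoglobulins together with a further test: "direct antiglobulin test have to be measured at screening and at occurrence of infusion related reactions". It also asks for more frequent sampling when there are relevant findings.

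Protocol 7.5 has a fallback: "Missing baseline laboratory values will be imputed by the respective values from the screening visit". SAP 7.8.2 uses the laboratory baseline for changes by visit, for transition tables, and to flag possible clinically significant abnormalities, defined for graded parameters as "laboratory values with a CTC grade ≥ 2 that have had an increase of ≥ 1 grade from baseline".

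**The concern.** A baseline has to be untouched by treatment. The laboratory sentence drops the one condition that secures this: it limits the calendar day but not the order of sample and infusion. Because laboratory data have their own sentence, a programmer would reasonably apply it in place of the general rule.

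At stake is the description of early laboratory change in patients who were sampled because something happened during or after the first infusion. For them a post-infusion value would be the reference for every later laboratory comparison. SAP 6.1 starts the on-treatment period on the date of first intake, so the same Day 1 value can also count as on-treatment and be compared with itself. Preliminary safety data are the trial's secondary objective, and protocol 2.3 promises close attention to immunogenic effects.

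**Working it through.** The plan states no figure on this point, so there is none to reproduce. The check applies the rule as written to the sampling patterns the protocol allows.

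**Is a post-infusion Day 1 sample realistic?** Yes. Protocol 6.1 keeps patients in hospital for at least 48 hours after the first infusion. Protocol 5.3.3 requires reaction samples and allows extra ones. Footnote 5 accepts safety laboratory results up to 72 hours old, so a patient may have no Day 1 pre-dose draw.

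**Does the protocol fix the timing?** Not for safety laboratory samples. ECG has a pre-dose window of 60 to 5 minutes before infusion (5.3.4). Vital signs have a pre-dose time point (5.3.2). Table 10.4: 1 gives times for PK, ADA, biomarkers, ECG and blood pressure. It has no column for safety laboratory samples.

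**What does the rule select?** Take illustrative values (assumed): 100 before the first infusion, 140 on Day 1 after it, 120 on Day 8. Change = value − baseline. The SAP does not say whether closeness is judged by date or by clock time, so both readings are shown.

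| Samples available | Rule | Baseline | Day 1 post-infusion change | Day 8 change |
|---|---|---|---|---|
| (a) Screening and Day 1 reaction only | Strictly before infusion | 100 | 140 − 100 = +40 | 120 − 100 = +20 |
| (a) | SAP, either reading | 140 | 140 − 140 = 0 | 120 − 140 = −20 |
| (b) Day 1 pre-dose (−1 h) and unscheduled post-infusion (+3 h) | Strictly before infusion | 100 | +40 | +20 |
| (b) | SAP, latest value dated on or before Day 1 | 140 | 0 | −20 |
| (b) | SAP, nearest in clock time | 100 | +40 | +20 |
| (c) Day 1 pre-dose only | Any | 100 | no such sample | +20 |

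Pattern (a) is that of immunoglobulins and the antiglobulin test after a first-infusion reaction. The reaction sample is both the latest and the nearest, so both readings give the same result. For a result recorded as a category, the equivalent is that no transition appears. A later value would exist for these tests only at a further reaction or an unscheduled draw. Its change is then shifted by 140 − 100 = 40, from +20 to −20. Protocol 7.5 does not help, because baseline is not missing.

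Pattern (b) can arise for routine safety laboratory values. The result depends on which Day 1 value is taken, and the SAP does not say. Pattern (c) is unaffected.

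**Grade-increase flag.** Suppose a graded parameter in pattern (b) is grade 0 before infusion and grade 2 after it on Day 1. Against the pre-dose value the rise is 2 − 0 = 2 grades and the flag is raised. Against the post-infusion value the rise is 2 − 2 = 0 and it is not.

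**How many patients?** The documents give no rate of first-infusion reactions. As pure assumption, with 25 treated patients and rate r, the expected number is 25r and the chance of at least one is 1 − (1 − r)^25:

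- r = 5%: 1.25 patients, 72%
- r = 10%: 2.5 patients, 93%
- r = 20%: 5.0 patients, 99.6%
- r = 30%: 7.5 patients, above 99.9%

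These figures show scale only; they are not predictions.

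**The case against.** The strongest reply is that a pre-dose baseline is plainly intended. The general rule in the same paragraph says so. Routine safety laboratory tests have one Day 1 entry, eligibility is confirmed that day, and the 72-hour allowance looks back from first treatment. All of this points to a pre-dose draw, and if that is the only Day 1 sample the rule does no harm. The SAP also cites a sponsor standard for laboratory data that we cannot see and that may settle same-day timing. Immunoglobulins and the antiglobulin test are not among the focus parameters in SAP 7.8.2, and the documents give no CTC grading for them. Clinically relevant laboratory changes are still recorded as adverse events (protocol 5.3.6.2), and immunogenicity has its own ADA assessment (5.6.2).

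Most of this stands and limits the consequence. It does not repair the sentence. Intent has to be inferred against the wording, and pattern (a) fails under every reading of that wording.

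A reader might infer more than the documents support:

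- **That blood pressure and ECG are affected too.** Protocol 5.3.2 does say for vital signs: "At day of administration two time points will be evaluated", one of them near the end of the infusion. But the general rule governs these variables and requires a value before administration. Allowing the same date does not remove that condition, and pre-dose time points are fixed.
- **That early laboratory changes are zeroed generally, or that the bias always runs towards no change.** Only the selected sample's own change becomes 0. Later changes are shifted, and in the example the Day 8 change reverses sign. Reactions confined to later infusions are unaffected.
- **That about 30% of patients are expected to react.** That figure in protocol 4.1.4 is a trigger for premedicating everyone. It is neither an expected rate nor specific to the first infusion.

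**Conclusion.** The point holds for laboratory data. As written, SAP 6.7 admits a post-infusion Day 1 value as baseline. For immunoglobulins and the direct antiglobulin test after a first-infusion reaction it selects one, and the change at the reaction is then exactly 0. For routine safety laboratory values the effect is conditional on a post-infusion Day 1 sample existing and being selected.

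The effect stays within descriptive laboratory change and shift tables and, for graded parameters, the grade-increase flag. A reader might wonder about the primary endpoint. The documents give no route to it: DLTs follow protocol 5.3, the MTD follows from DLT counts through the Bayesian model, and neither takes the SAP laboratory baseline as input.

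The conclusion rests on reading the laboratory sentence literally and on no unseen sponsor standard overriding it. How many patients are affected is unknown. The sentence should be corrected before the laboratory tables are produced, because the rule gives a wrong result in an identifiable case and costs little to change.

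**What to change.** Replace the laboratory sentence in SAP 6.7 with a rule to this effect:

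- Laboratory baseline is the last non-missing value, by date and time, before the start of the first infusion; otherwise the screening value.
- If the sampling time is missing, a Day 1 value is accepted only if it is the scheduled Visit 1 sample.
- Unscheduled or reaction samples on Day 1 are post-baseline.

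In patterns (a) and (b) this restores the changes of +40 on Day 1 and +20 on Day 8, and it removes the need for a tie rule. The second item assumes that the scheduled Visit 1 sample is drawn before the infusion. The documents suggest this but do not state it, so the sponsor should confirm it.

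The cost is one date-time comparison in the derivation, and a few patients falling back to screening values. No blood pressure, ECG, DLT or model specification needs to change.
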